**Specific Aim 1:** Demonstrate BAT mass detection in human subjects. For this aim we will implement hyperpolarized xenon imaging on our clinical scanner and we will compare the images obtained before stimulation of BAT thermogenesis with those obtained during stimulation of BAT thermogenesis. Our working hypothesis is that, during stimulation of BAT thermogenesis the lipophilic gas will accumulate in the highly perfused BAT tissue enabling us to clearly delineate it.

**Specific Aim 2:** Demonstrate detection of BAT thermogenesis in humans. For this aim we will measure BAT temperature by measuring the chemical shift of lipid-dissolved xenon. Our working hypothesis is that, during stimulation of BAT thermogenic activity, changes in BAT temperature would be detected as a shift in the resonance frequency of lipid-dissolved xenon.

By the end of the proposed project we expect to have demonstrated the feasibility of HP xenon

MRI detection of human BAT mass and thermogenic activity. These studies will also provide preliminary data for powering a future clinical trial with which we aim to investigate the incidence and activity of this tissue in the human population.

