same protocol will be followed during stimulation of BAT thermogenesis, which will be achieved by an MR compatible water cooling-blanket ( $\sim 15^{\circ}\text{C}$  circulating water temperature), which will be positioned on the lower abdomen/upper leg part of the subjects. The ability to detect BAT by hyperpolarized xenon gas relies on the enhancement in blood flow to this tissue that occurs during stimulation of thermogenic activity. The magnitude of this enhancement seems to be the same, irrespective of the species and of the modality of stimulation of BAT thermogenesis (NE injection of mild cold exposure). Therefore we expect to detect a similar enhancement in the MR signal from xenon dissolved in human BAT. In addition, the use of enriched xenon versus naturally abundant xenon will compensate for the possible loss in xenon polarization during blood transit time. Pre and post stimulation scans will be compared with Matlab to detect differences of more than 5% in the intensity of the dissolved phase xenon images. Detectable BAT volume will be calculated as the sum of pixels whose intensity rose by more than 5% during cold stimulation multiplied by the pixel volume ( $1 \text{ mm}^3$ ). Data will be analyzed using JMP Pro-9.0.0 software (SAS Institute). All P values presented will be two-tailed, and values less than 0.05 will be considered to indicate statistical significance. According to previous studies done in human brain and considering the increase in blood perfusion that occurs in BAT during cold stimulation as well as the higher solubility of xenon in fatty tissues, we expect to be able to obtain images with a resolution of  $0.3 \times 0.3 \text{ cm}$ , high enough to differentiate BAT from the surrounding tissues.

**Aim 2:** Demonstrate detection of BAT thermogenesis in humans.

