Dynamic spectroscopy data have shown the possibility to track BAT temperature over time by measurement of the chemical shift of lipid-dissolved xenon. We demonstrated for the first time MR thermometry by hyperpolarized xenon gas. This method is based on the temperature dependence of the chemical shift of lipid dissolved xenon, which we measured for the first time *in vivo* to be  $-0.2 \text{ ppm}^{\circ}\text{C}$ , (Fig 2.a), i.e. 20 times larger than that of water protons currently used for MR thermometry in lean tissues. This higher sensitivity of lipid-dissolved xenon to temperature, coupled with the lower gyromagnetic ratio of xenon (which makes xenon less sensitive to possible magnetic field in homogeneities present in fatty tissues), allowed us to detect BAT thermogenic activity in mice (Fig.2.b). To this end we will acquire dynamic spectroscopy data from xenon dissolved in BAT during stimulation of BAT thermogenesis by mild cold exposure. During these scans we will track the resonance frequency of lipid-dissolved xenon to detect changes in BAT temperature during thermogenic activity. Although in humans we expect temperature changes less than  $2^{\circ}\text{C}$ , the high sensitivity of xenon to temperature and the narrow line width can allow us to detect changes as small as  $0.2^{\circ}\text{C}$ .

**Fig.2** a) Linear temperature shift of the lipi-dissolved xenon frequency as acquired *in vivo* in an obese mouse. b. Thermogenic activity as detected by hyperpolarized xenon gas. The graph shows the resonance frequency shift of lipid-dissolved xenon and the corresponding shift in BAT temperature right after injection of NE.

For these studies the subject will inhale 4 doses of 1L each of xenon during mild cold exposure, achieved with a water cooling blanket. After inhalation, the subject will be asked to hold his breath for 15-20 seconds, during which we will trigger the acquisition of xenon spectra. The spectra will then be fitted with homemade Matlab routines to extract lipid-dissolved xenon resonance frequency that will be used to detect any change in BAT temperature.

The change in BAT temperature will then be analyzed as function of BMI to establish whether or not there is an association between BMI and BAT temperature increase (Pearson correlation and Spearman correlation coefficient calculation).

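### Neither aim has a stated analysis that could show its cold-response hypothesis false: Aim 1 counts only pixels that rose, and Aim 2's only named statistic is a correlation with BMI

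*Combined protocol and SAP*

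**What the plan says.** The Specific Aims state one working hypothesis per aim, each about what happens within a subject under cold stimulation. For Aim 1: "during stimulation of BAT thermogenesis the lipophilic gas will accumulate in the highly perfused BAT tissue enabling us to clearly delineate it". For Aim 2: "changes in BAT temperature would be detected as a shift in the resonance frequency of lipid-dissolved xenon".

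The analysis text in the Approach section is short.

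- **Aim 1.** Images taken before and during cooling are compared for intensity differences above 5%. The one derived quantity is a volume: "Detectable BAT volume will be calculated as the sum of pixels whose intensity rose by more than 5% during cold stimulation". That sum is then scaled by the size of a pixel. The same paragraph sets a general rule, "All P values presented will be two-tailed, and values less than 0.05 will be considered to indicate statistical significance", without attaching it to any test.
- **Aim 2.** Spectra are fitted to extract the lipid-dissolved xenon frequency, which is to be used to detect any temperature change. No test or threshold for a positive subject is given. The four doses are described as inhaled during mild cold exposure, and no spectrum before cooling is described. The only named statistical procedure is "Pearson correlation and Spearman correlation coefficient calculation", and its stated purpose concerns BMI: "The change in BAT temperature will then be analyzed as function of BMI to establish whether or not there is an association".

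The closing paragraphs of the Approach call this a feasibility study that will estimate standard deviations for future trials, and list the BMI association among the questions for those trials. With 12 subjects per aim, they and section F (Number Justification) expect at least 9 positive subjects if prevalence is 90% and at least 3 if it is 50%.

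**The concern.** An analysis supports a hypothesis only if it could have come out against it. The Aim 1 volume discards every pixel that fell, so it cannot be negative and is close to certain to be positive whenever the images contain noise. The Aim 2 correlation asks how temperature change varies between subjects, not whether temperature changed.

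The study expects to have demonstrated the feasibility of detecting both BAT mass and thermogenic activity. If the reported outputs are a positive volume and a BMI coefficient, neither shows that cooling produced the response. The standard deviations wanted for future trials also depend on one defined change per subject, and the plan does not define it.

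**Working it through.** **1. The plan's own figure.** Inputs: n = 12 per aim, prevalence 90% or 50% (end of the Approach; section F). With X binomial:

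- P(X ≥ 9 | 12, 0.9) = 0.974 and P(X ≥ 10) = 0.889
- P(X ≥ 3 | 12, 0.5) = 0.981 and P(X ≥ 4) = 0.927

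So 9 and 3 are the largest counts reached with at least 95% probability, and the stated figures reproduce. They are expectations about how many subjects will be positive. They are not stated as a success rule, and they assume that each subject can be classified correctly.

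**2. Aim 1: pixels that pass with no true change.** Input from the plan: the 5% threshold. Assumed, because the documents give no noise level: independent normal noise, equal in both images, with per-pixel signal-to-noise ratio S. A pixel passes if the second reading exceeds 1.05 times the first. With signal 1 and noise SD 1/S, the quantity (second − 1.05 × first) has mean −0.05 and SD √(1 + 1.05²)/S = 1.45/S. Hence

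P(pass) = P(Z > 0.05 × S / 1.45).

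| S (assumed) | z | Pixels passing with no change |
|---|---|---|
| 10 | 0.345 | 37% |
| 20 | 0.690 | 25% |
| 50 | 1.724 | 4% |

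A volume that sums these pixels is positive without any cold response. A signed mean over the same pixels would centre on zero.

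**3. Aim 2: what a correlation can see.** Both coefficients are unchanged when a constant is added to every outcome: Pearson uses deviations from the mean, Spearman uses ranks. In one simulated data set of 12 subjects:

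| Warming added to all | Pearson p | Spearman p | One-sample t-test p |
|---|---|---|---|
| 0 °C | 0.568 | 0.931 | 0.79 |
| 1 °C | 0.568 | 0.931 | 9 × 10⁻⁵ |
| 2 °C | 0.568 | 0.931 | 1 × 10⁻⁷ |

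The BMI statistic is therefore silent on the Aim 2 hypothesis, whatever the true effect.

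**4. What 12 subjects give for a signed change.** The 95% interval for the mean has half-width 2.201 × SD/√12 = 0.64 SD. Power of a two-sided one-sample t-test at 0.05 (noncentral t, 11 df), over assumed ratios of mean to SD because the documents give no SD:

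| Mean/SD | 0.5 | 0.8 | 0.9 | 1.0 | 1.5 |
|---|---|---|---|---|---|
| Power | 35% | 71% | 81% | 88% | >99% |

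These figures treat every subject as a responder. If responders change by +1 SD and the others by zero, the mean is p and the variance is 1 + p(1 − p), where p is the prevalence. The ratio of mean to SD is 0.9/√1.09 = 0.86 at 90% prevalence and 0.5/√1.25 = 0.45 at 50%. Simulated power is about 78% and 29%.

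**The case against.** The strongest reply is that this is a feasibility study. It frames success as detection in individual subjects, estimation of standard deviations and expected counts of positives, and such a study needs no tested primary contrast. A pre/post test may also be intended under the general p-value rule. Much of this stands: a descriptive analysis would be legitimate, and the expected counts are computed correctly. It does not close the gap. A count of positives needs a definition of a positive subject. For Aim 1 the 5% rule admits noise pixels and no minimum volume is set; for Aim 2 there is no definition. The text says that changes as small as 0.2 °C can be detected, but does not make that a classification rule. If a pre/post test is intended, it is not named.

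A reader might infer more: that the BMI correlation is the study's only significance test and so decides Aim 2, allowing a clear warming to end as a null result or the reverse. The documents do not support that. The correlation is described as a coefficient calculation on an association, the p-value rule stands in the Aim 1 text and is tied to no test, and the BMI question is placed with future trials. Nor is there ground to claim an inflated error rate from testing both warming and BMI, since the plan names no test of warming. And nobody proposes to test the Aim 1 volume against zero; the objection is to what that volume can show.

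**Conclusion.** The point holds as a gap between aims and analyses: the stated outputs do not answer either aim's own question. It does not show that a wrong test decides the study, and it does not undermine the design or the sample size.

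That the correlation ignores mean warming is exact and needs no assumption. That the rising-pixel volume is biased upward needs only some noise in the images; its size (4% to 37% of pixels) rests on the assumed signal-to-noise ratio and on independent, equal noise. The power figures rest on normal data and assumed ratios of mean to SD.

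**What to change.** **Aim 1 (analysis text in the Approach).** For each subject, report the signed change in dissolved-xenon signal, during minus before cooling, over a supraclavicular region fixed in advance on the anatomical proton images, counting pixels that fell as well as those that rose. Summarise as a mean with SD and 95% confidence interval and one paired two-sided test at 0.05. Keep the rising-pixel volume as a descriptive result.

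**Aim 2 (analysis text in the Approach).** For each subject, report one signed temperature change from a named reference reading, as a mean with SD and 95% confidence interval and one two-sided one-sample test at 0.05. State which acquisition is the reference. If all acquisitions are made under cooling, limit the claim to change during cooling.

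**BMI.** Label the correlation exploratory and report it as a coefficient with its confidence interval.

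**Both aims.** Report the count of positive subjects alongside, with a definition of a positive subject written down beforehand.

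**Cost.** A few sentences and no extra subjects. The Aim 1 change uses scans already planned; for Aim 2 this depends on which reading can serve as reference, which the documents leave open. There are three downsides. A BMI result with p below 0.05 could no longer be presented as a main finding. A regional mean dilutes small, scattered depots. Power drops when not everyone responds, which is why the counts should stay. The signed change removes the upward bias from noise, but not any systematic difference between the two scans.

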**INNOVATION:** MRI with hyperpolarized xenon-129 is a technique that is been used extensively in humans to detect lung ventilation function. Here we propose for the first time to use hyperpolarized xenon gas MRI to detect BAT. Xenon is an ideal BAT probe for several reasons: A) the solubility of xenon in fatty tissue is 10 times higher than in lean tissues or blood. This means that circulating xenon naturally diffuses into BAT, enabling adequate SNR for imaging. B) Xenon is an ideal blood perfusion tracer, and therefore ideally suited to detect the increase in blood flow to BAT that occurs during stimulation of BAT thermogenesis. C)

Because xenon is not intrinsic to biological tissue, HP  $^{129}\text{Xe}$  can produce background free maps of human BAT. D) The temperature sensitivity of lipid-dissolved xenon will enable us to directly measure BAT temperature and monitor thermogenic activity in real time.

*This research is innovative as it uses an entirely different approach to investigate BAT. To our knowledge we are the very first group to use hyperpolarized xenon gas to detect BAT mass and to have demonstrated HP xenon MR thermometry of fatty tissues.*

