This feasibility study will allow us to estimate the standard deviation for the increase in signal from xenon dissolved in BAT and for the increase in BAT temperature that will then be used to power future trials to investigate the incident of this tissue in the healthy human population and the association between BMI and BAT thermogenic activity. For these aims we plan on enrolling a total of 24 healthy subjects (12 for aim 1 and 12 for aim 2) with a BMI ranging between 18 and 28. Twelve is the minimum sample size recommended in the absence of prior information on which to base our sample size calculation. With 12 subjects per group we should be able to obtain positive results (with a 95% confidence interval) on at least 9 subjects if the true prevalence of BAT is 90% (expected prevalence), and on at least 3 subjects if the true prevalence of BAT is much smaller and close to 50% (estimated by FDG-PET scans).

By the end of the study we expect to have fully assessed the potential of HP xenon to detect BAT mass and activity and to have developed an imaging protocol that can be used in studies aimed to investigate the prevalence of this tissue in humans, its connection with other metabolic diseases such as diabetes, and to study the response to treatments aimed to counteract obesity by increasing BAT mass and or function.

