#### **F. Number Justification**

A total of 24 subjects will be enrolled in this study. 12 to complete specific aim 1 and 12 to complete specific aim 2. Twelve is the minimum sample size recommended in absence of prior information on which to base our sample size calculation(2). With 12 subjects per group we should be able to obtain positive results (with a 95% confidence interval) on at least 9 subjects if the true prevalence of BAT is 90%(3) (expected prevalence), and on at least 3 subjects if the true prevalence of BAT is much smaller and close to 50% (estimated by FDG-PET scans(4).

1. B. Driehuys *et al.*, Chronic Obstructive Pulmonary Disease: Safety and Tolerability of Hyperpolarized  $^{129}\text{Xe}$  MR Imaging in Healthy Volunteers and Patients. *Radiology* **262**, 279 (January 1, 2012, 2012).
2. S. A. Julious, Sample size of 12 per group rule of thumb for a pilot study. *Pharmaceutical Statistics* **4**, 287 (2005).
3. W. D. van Marken Lichtenbelt *et al.*, Cold-Activated Brown Adipose Tissue in Healthy Men. *New England Journal of Medicine* **360**, 1500 (2009).

4. M. Saito *et al.*, High Incidence of Metabolically Active Brown Adipose Tissue in Healthy Adult Humans: Effects of Cold Exposure and Adiposity. *Diabetes* **58**, 1526 (July 1, 2009, 2009).

**DETAILED BUDGET FOR INITIAL BUDGET PERIOD  
DIRECT COSTS ONLY**
FROM  
06/01/2014THROUGH  
05/31/2015List PERSONNEL (*Applicant organization only*)

Use Cal, Acad, or Summer to Enter Months Devoted to Project

Enter Dollar Amounts Requested (*omit cents*) for Salary Requested and Fringe Benefits

NAME	ROLE ON PROJECT	Cal. Mnths	Acad. Mnths	Summer Mnths	INST.BASE SALARY	SALARY REQUESTED	FRINGE BENEFITS	TOTAL
	PD/PI							
Research Assistant		4	4		24,025	7,600	1,040	8,640
SUBTOTALS →						7,600	1,040	8,640

CONSULTANT COSTS

EQUIPMENT (*Itemize*)

SUPPLIES ( Itemize by category )	19,968
3T scan time	12,240
Enriched Xenon gas mixture	
Volunteer time	1,440

TRAVEL

INPATIENT CARE COSTS

OUTPATIENT CARE COSTS

ALTERATIONS AND RENOVATIONS (*Itemize by category*)OTHER EXPENSES (*Itemize by category*)

CONSORTIUM/CONTRACTUAL COSTS	DIRECT COSTS	
SUBTOTAL DIRECT COSTS FOR INITIAL BUDGET PERIOD ( Item 7a, Face Page )	\$	42,288
CONSORTIUM/CONTRACTUAL COSTS	FACILITIES AND ADMINISTRATIVE COSTS	
TOTAL DIRECT COSTS FOR INITIAL BUDGET PERIOD	\$	42,288

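### Aim 2 reads brown-fat temperature from a lipid-xenon signal in 12 subjects with no clearly planned BAT map, so the signal is not shown to come from brown fat

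*Combined protocol and SAP*

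**What the plan says.** The sample-size paragraph that closes the APPROACH section reads "we plan on enrolling a total of 24 healthy subjects (12 for aim 1 and 12 for aim 2"), and Section F repeats "12 to complete specific aim 1 and 12 to complete specific aim 2".

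Under APPROACH, Aim 2, subjects inhale four doses during mild cooling. "The spectra will then be fitted with homemade Matlab routines to extract lipid-dissolved xenon resonance frequency", and the change in that frequency is taken as the change in BAT temperature. That change is correlated with BMI (Pearson and Spearman). The SD of the temperature increase is to be used to power later trials.

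The only rule that identifies BAT belongs to Aim 1: "Detectable BAT volume will be calculated as the sum of pixels whose intensity rose by more than 5% during cold stimulation". Aim 1 subjects are listed for both xenon spectroscopy and xenon imaging, before and during cooling. Localisation in Aim 2 comes from placing the surface coil over the supraclavicular area; no voxel is specified.

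The INNOVATION section notes that "the solubility of xenon in fatty tissue is 10 times higher than in lean tissues or blood", which is a property of fat in general. The sample-size paragraph looks for positive results "on at least 9 subjects if the true prevalence of BAT is 90" per cent, labelled the expected prevalence, and "on at least 3 subjects if the true prevalence of BAT is much smaller and close to 50" per cent, taken from FDG-PET scans.

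**The concern.** Aim 2 sets out to demonstrate detection of BAT thermogenesis. That requires evidence that the fitted lipid peak comes from brown fat. In the group where temperature is measured, no map of BAT is clearly planned. In the group where BAT is mapped, no temperature analysis is planned. Nothing joins the two.

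Two outputs are at stake. The first is interpretation: a flat frequency could reflect no BAT, BAT that did not activate, or a method that failed, and a shift could come from other fat near the coil. The second is what is carried forward: the BMI correlation and the SD for future trials could reflect who has BAT as well as how much it heats.

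**Working it through.** **1. Are the groups separate?** Both statements of sample size split 24 into 12 and 12. In the budget, 48 h of scan time is 24 sessions of 2 h, and 48 L of enriched xenon is 24 × 2 L. Some bracketed sums there disagree with these totals (3 h × 10 subjects = 30 h; 2 L × 12 = 24 L), so the budget is only supporting evidence. One text leaves room for doubt: the general scanning procedure in Section A says that imaging will be performed, without limiting this to Aim 1.

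**2. The plan's own figures.** With X ~ Binomial(12, p), take the largest r with P(X ≥ r) ≥ 0.95.
- p = 0.90: P(X ≥ 9) = 0.9744 and P(X ≥ 10) = 0.8891, so r = 9.
- p = 0.50: P(X ≥ 3) = 0.9807 and P(X ≥ 4) = 0.9270, so r = 3.

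Both stated minima are reproduced.

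**3. Subjects without BAT among the 12 in Aim 2.** The expected number is 12(1 − p), and the chance of at least one is 1 − p^12.
- p = 0.90: 12 × 0.10 = 1.2; 1 − 0.9^12 = 0.718.
- p = 0.50: 12 × 0.50 = 6; 1 − 0.5^12 = 0.9998.

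**4. Effect on the mean, SD and BMI correlation (illustration).** The plan says only that changes below 2 °C are expected and gives no SD. Assume a mean rise of 1 °C in carriers with SD s, and exactly 0 in non-carriers. Then:
- mean = p × 1, which is 0.90 °C at 90% and 0.50 °C at 50%;
- SD = √[p·s² + p(1 − p)·1²];
- if BAT status is unrelated to BMI, the carriers' BMI correlation is multiplied by p·s/SD.

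| Assumed carrier SD | SD at 90% | SD at 50% | Factor at 90% | Factor at 50% |
|---|---|---|---|---|
| 0.3 | 0.41 | 0.54 | 0.65 | 0.28 |
| 0.5 | 0.56 | 0.61 | 0.80 | 0.41 |
| 1.0 | 0.99 | 0.87 | 0.90 | 0.58 |

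For example, with s = 0.5 and p = 0.9, SD = √(0.225 + 0.090) = 0.56 and the factor is 0.9 × 0.5 / 0.561 = 0.80. With s = 1.0 the pooled SD is not inflated; at 50% it falls. If BAT presence is itself related to BMI, these factors do not apply, and the correlation could partly reflect presence.

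**5. Would restricting Aim 2 to carriers help?** The plan's significance rule is "All P values presented will be two-tailed, and values less than 0.05 will be considered to indicate statistical significance". The critical |r| is t/√(n − 2 + t²), with t the 97.5% point on n − 2 degrees of freedom: 0.576 at n = 12, 0.666 at n = 9 and 0.997 at n = 3. At the plan's minimum for 50% prevalence, a subset correlation would be close to unusable.

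**The case against.** The strongest reply is that localisation is not absent. The coil sits over the supraclavicular area. The documents' case for specificity rests on perfusion as well as solubility: xenon is presented as a blood-flow tracer, and a more than 10-fold signal gain on stimulation is reported in rodents. This stands. A reader might infer that the Aim 2 reading cannot be tied to brown fat at all, and the documents do not support that. They support a regional signal whose brown-fat origin is a hypothesis under test and is not verified in these subjects.

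A reader might also infer that a subject without BAT will be analysed as BAT that did not warm. The plan gives no rule. Such a subject might score zero, show a shift from other fat, or drop out for lack of a usable peak. The zero in the illustration is an assumption.

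Three further points stand in part.
- Only 90% is labelled as expected. The 50% comes from FDG-PET, which the SIGNIFICANCE section says underestimates BAT activity, so it is a pessimistic case.
- If later trials enrol unselected healthy volunteers, the all-subject SD is the relevant one. But the plan also wants to study BMI against BAT thermogenic activity, and there the mixing matters.
- This is a small feasibility study, and assigning different subjects to the two aims is a legitimate choice. That limits the weight of the point but leaves the missing link in place.

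Adding one cooled xenon image to Aim 2 may look like the natural remedy. It would not work: the 5% rule needs a baseline image, and signal in supraclavicular fat alone does not identify BAT. It would also be hard to fit in, since a 10 s wait plus about 10 s of imaging already fills the longest stated breath-hold of 20 s.

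**Conclusion.** The concern holds in limited form. Aim 2 labels a regional lipid-xenon frequency as BAT temperature in subjects for whom no BAT map is clearly planned, and the plan cannot separate no BAT, inactive BAT and method failure. On its own prevalences, 1.2 of 12 subjects (expected case) or 6 of 12 (FDG-PET case) would lack BAT.

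The counts rest on the plan's figures alone. The effect on the mean, SD and correlation rests on an assumed 1 °C rise in carriers and none in others. On those terms the mean falls by a tenth at 90% prevalence and by half at 50%. A reader might infer that the SD for future trials is bound to be inflated, but the table shows that its direction depends on the carrier SD, which nobody yet knows. The point merits a change to the analysis plan and its wording, not a redesign.

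**What to change.** 1. **Link frequency to BAT in Aim 1.** Use the xenon spectroscopy already listed there or, if its timing does not suit, a brief low-flip-angle spectrum late in the 10 s wait before each image, at baseline and during cooling. Late is preferable because xenon is still travelling from the lungs earlier in the wait. Fit the lipid-dissolved frequency with the Aim 2 routine and report each subject's before/during change against that subject's map of pixels rising more than 5%. Present this as the evidence linking frequency shift to BAT, and note that the image rule is itself under test and has no independent reference.
2. **Treat the link as descriptive.** At 90% prevalence there is a 0.9^12 = 28% chance that all 12 Aim 1 subjects have BAT, leaving no non-carriers for contrast.
3. **Keep the all-subject Aim 2 result and BMI correlation as planned**, described as regional lipid-dissolved xenon temperature not confirmed as BAT.
4. **Clarify the wording.** State whether Aim 2 subjects are imaged and how a subject without a usable lipid peak is handled.
5. **Reconcile the passages that conflict.** Aim 2 doses are four of 1 L under APPROACH and four of 0.5 L in the budget (with 2 L per imaging subject, 12 × 2 + 12 × 4 = 72 L against 12 × 2 + 12 × 2 = 48 L). Breath-holds are 15–20 s under APPROACH and 10–15 s in the Section A scanning procedure.

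The cost is analysis time, protocol wording and possibly a sequence edit, with no extra dose or visit. Any added pulses use some polarization, so image signal-to-noise falls slightly.
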